 - b) Usability Assessment: Assess the model's usability by involving healthcare professionals in the evaluation process, measuring integration into clinical workflows, result interpretability, and time efficiency during histopathology examinations.
 - c) Impact on Early Detection: Investigate the AI model's impact on early breast cancer detection, analyzing its contribution to identifying cancer types at earlier stages for potentially improved patient outcomes.
 - d) Generalizability: Evaluate the model's generalizability across diverse datasets, including local sources, assessing its performance in different regions and healthcare settings for broader clinical applicability.
 - e) Impact on Patient Outcomes: Examine the AI model's impact on patient outcomes, such as reduced diagnosis time, increased accuracy in cancer type identification, and enhanced treatment planning, considering potential benefits to patient well-being and satisfaction.
 - f) Clinical Decision Support: Evaluate the model's effectiveness as a clinical decision support tool, measuring its contribution to accurate diagnoses and treatment plans during histopathology examinations.

Through these objectives, our research aims to advance breast cancer diagnosis, providing a comprehensive solution that integrates seamlessly with clinical practices and positively influences patient outcomes.

- **Rationale:** Histopathology images contain valuable information about tissue structure, but manual interpretation can be subjective and time-intensive. Deep learning offers a promising solution by automatically learning complex patterns, potentially improving the accuracy and efficiency of breast cancer classification. This research aims to leverage deep neural networks to analyze extensive datasets of histopathology images, distinguishing between invasive and noninvasive breast cancer with high accuracy. Automating this classification process aims to reduce human error, expedite diagnoses, and support personalized treatment approaches. Ultimately, the goal is to refine breast cancer diagnosis, enabling earlier intervention and better patient outcomes.

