b) **Sample size calculation:** Following the methodology of sample size calculation to evaluate diagnostic performance (for algorithms in this case), we use the following method of calculation for a target sensitivity and specificity incorporating disease prevalence [7]:

$$N_{sen} \geq \frac{Z^2(1-\alpha)/2 \times sen(1 - sen)}{c^2 \times p}$$

$$N_{spec} \geq \frac{Z^2(1-\alpha)/2 \times spec(1 - spec)}{c^2 \times (1 - p)}$$

N_{sen} = Required sample size for sensitivity, sen
 N_{spec} = Required sample size for specificity, $spec$
 α = Confidence level
 $Z^2(1-\alpha)/2$ = The Z-score for the confidence level α
 p = Prevalence of breast cancer
 c = Confidence interval
 sen = Estimated sensitivity
 $spec$ = Estimated specificity

- The final sample size N is calculated based on the larger of the two values N_{sen} and N_{spec} . In this study, as we are using deep learning techniques, we need the medical image samples to reflect the various cancerous, precancerous and normal cases. For our analysis, we assume an 80% confidence level ($\alpha = 0.80$) and prevalence of breast cancer for self-reported instances, $p = 0.261$ [23]. A confidence interval of 5% is selected ($c = 0.05$). We estimate the sensitivity and specificity of our algorithms to be at 75% ($sen = 0.75$ and $spec = 0.75$). Using these values, we obtain the sample size values: $N_{sen} = 471$ and $N_{spec} = 166$. Since $N_{sen} > N_{spec}$, the final sample size for the study will be:

$$N = N_{sen} = 471$$

We can set a target of $N = 500$.

c) Procedures: During the prospective phase of the study, data collection will occur in clinical settings. Eligible patients will be approached during clinic visits and presented with a consent form for their review. Upon agreement, each participant will be assigned a unique identifier to maintain data integrity and ensure patient anonymity. Subsequently, patients will provide essential clinical information. Healthcare professionals will conduct histopathological examinations, and specialized equipment available in the clinic will be used to capture images of the breast region. This method guarantees the collection of non-identifiable data, unique data identifiers, and informed consent directly within the clinical setting, meeting the specific requirements of histopathological breast cancer screening.

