In the retrospective phase of the study, additional data will be retrieved from the clinic's database of prior screenings. Due to the retrospective nature, obtaining consent from individual patients is impractical. To address privacy concerns, any personally identifiable patient information will be systematically excluded from the collected data. This ensures compliance with privacy standards while leveraging valuable information from past screenings. While informed consent cannot be obtained for this dataset, the study will strictly adhere to ethical guidelines and prioritize patient privacy during the data extraction process from the clinic's database.

d) Methods of Data Collection:

- Patient ID (unique identification number)
- Date & Time of data input
- Age
- Histopathological breast image data
- Region of Interest (ROI) Annotations:
 - Lesion size
 - Provisional diagnosis
 - Suggested management (e.g., routine screening, biopsy, etc.)
 - Patient's relevant medical/surgical history
- Additional Information (if available):
 - Relevant diagnostic test results
 - Reproductive history

The hematoxylin and eosin (H&E) stained images obtained from histopathological assessment, along with relevant metadata, will significantly contribute to algorithm design and image analysis. These

images' standard test status and corresponding results will serve as the ground truth for our detection algorithm.

e) **Data Interpretation:** Following the completion of data collection, exploratory data analysis will be conducted to assess patient distribution across various parameters, including transformation zone type, histopathology, and relevant clinical factors. Subsequently, a balanced dataset will be curated to ensure fair representation of image samples.

This curated dataset will serve as the foundation for training and evaluating the artificial intelligence (AI) algorithm developed for automatic classification and detection of abnormalities in histopathological breast screening cases. The trained model will generate predictions regarding the presence or absence of abnormalities in the breast images.

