To validate the accuracy and clinical relevance of the algorithm's predictions, the results will undergo verification and analysis in collaboration with expert histopathologists. Their insights will be invaluable in refining the automatic algorithm, thereby improving its precision in classifying and detecting potential abnormalities during histopathological breast screenings.

f) **Statistical Analysis:** Once the dataset becomes available, statistical analysis will center on evaluating the performance of the developed artificial intelligence algorithms for automatic classification and detection of abnormalities in histopathological breast screening cases. Key metrics such as sensitivity, specificity, precision, recall, F-1 score, and overall accuracy will be utilized for rigorous evaluation. To ensure robustness, experiments involving n-fold cross-validation will be performed, with mean values and standard deviations of performance metrics calculated. This analysis will conclude with a comparative assessment of various deep learning models, assessing their effectiveness in the automatic classification task.

Utilization of Results: The study results will be pivotal in the development and assessment of an automatic detection algorithm for breast cancer screening, with the following primary objectives:

- a) **Automatic Detection:** Evaluate and detect potential abnormalities in histopathological images, furnishing an automated screening tool for efficient identification of breast cancer risk.
- b) **Clinical Decision Support:** Aid healthcare professionals by furnishing an automated analysis to assist in prioritizing treatment strategies and making informed clinical decisions based on the algorithm's findings.

c) Systematic Data Storage: Enable systematic storage of histopathological images and pertinent metadata to bolster ongoing research efforts, all while safeguarding individuals' privacy during the automated detection process.

These outcomes are poised to significantly enhance the efficiency and accuracy of breast cancer screening, offering valuable support to healthcare professionals in Bangladesh.

- **Facilities:** In the case of collecting data from histopathological breast cancer screening, no additional facilities are required except those the clinics are already equipped with (e.g. image acquisition and data storage capacity).

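### Diagnosis time, treatment planning and decision support (objectives e and f), and the causal wording of (c), need clinicians to use the AI, which neither study phase describes

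*Protocol*

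**What the plan says.** The Objectives section of the protocol lists six lettered aims. Four of them go, in whole or part, beyond how well the algorithm classifies images:

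- (b) Usability, by involving healthcare professionals and "measuring integration into clinical workflows, result interpretability, and time efficiency during histopathology examinations".
- (c) The model's "impact on early breast cancer detection, analyzing its contribution to identifying cancer types at earlier stages".
- (e) Its "impact on patient outcomes, such as reduced diagnosis time, increased accuracy in cancer type identification, and enhanced treatment planning".
- (f) Its value as decision support, "measuring its contribution to accurate diagnoses and treatment plans during histopathology examinations".

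Methodology c) Procedures describes two phases. In the prospective one, after consent and collection of clinical information, "Healthcare professionals will conduct histopathological examinations, and specialized equipment available in the clinic will be used to capture images of the breast region". For the other: "In the retrospective phase of the study, additional data will be retrieved from" the clinic's stored records of earlier screenings.

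Methodology b) sizes the study "for a target sensitivity and specificity incorporating disease prevalence". Methodology f) lists classification metrics with cross-validation and adds: "This analysis will conclude with a comparative assessment of various deep learning models". Methodology e) has expert histopathologists review the predictions, first to validate their accuracy and clinical relevance and then to help refine the algorithm. Methodology a) states the primary aim as the algorithm's ability to tell the patient categories apart from image data.

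**The concern.** A shorter time to diagnosis, better treatment planning, or a contribution to decisions can be observed only if somebody makes a diagnosis or a plan with the AI output in hand. To call the result reduced or enhanced also needs the same task done without it. If the protocol has neither, the objectives promise results that the design cannot deliver. The practical risk is at reporting: good sensitivity and specificity could be presented as evidence of faster diagnosis, better treatment plans or earlier detection, when none of these was measured.

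**Working it through.** **1. Objectives set against procedures, data and analysis**

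- *Use of the AI by clinicians.* The prospective phase contains consent, an identifier, clinical information, examination and image capture. The retrospective phase concerns examinations already finished. Neither includes a step in which a clinician sees AI output for a case being diagnosed.
- *Data items (Methodology d).* The list has no reading time, time to diagnosis, or indicator of decisions made with or without AI. The one time item is the date and time of data input, a data-entry stamp. Provisional diagnosis and suggested management are listed, but not recorded with and without AI.
- *Comparison (Methodology f).* The only one named is between deep learning models.
- *Expert review (Methodology e).* Histopathologists assess predictions already made. This can inform clinical relevance and interpretability. It is not use during an examination.
- *Activity chart (Flow Chart).* It shows four activities over six months: an initial algorithm on public data, collection, homogenization, and processing with analysis. None is an aided-reading or usability activity.
- *Utilization of Results.* Decision support appears here as a use of the findings, with no step that measures it.

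**2. What the sample size covers**

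Inputs from Methodology b): 80% confidence, sensitivity = specificity = 0.75, c = 0.05, p = 0.261. The two-sided 80% z is 1.2816, and z² = 1.6424.

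- N_sen = 1.6424 × 0.75 × 0.25 / (0.05² × 0.261) = 471.9
- N_spec = 1.6424 × 0.75 × 0.25 / (0.05² × 0.739) = 166.7

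With z rounded to 1.28 these become 470.8 and 166.3, so the stated 471 and 166 are reproduced. The inputs contain no comparator rate, difference or power. The target of 500 therefore rests on the precision of stand-alone sensitivity and specificity.

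**3. What is left for (c) if it is read as accuracy on in situ cases**

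The Summary calls in situ disease an early stage and puts invasive disease at about 70% of breast cancers. A 30% in situ share in this sample is an assumption, as is a cancer fraction equal to the sizing prevalence.

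- Expected cancers: 500 × 0.261 = 130.5
- Expected in situ cases: 130.5 × 0.30 = 39.15
- 80% half-width at 75% sensitivity: 1.2816 × √(0.1875 / 39.15) = 0.089
- 95% half-width: 1.96 × √(0.1875 / 39.15) = 0.136
- For all cancers together, the 80% half-width is 1.2816 × √(0.1875 / 130.5) = 0.049, in line with the planned 0.05

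Range for the assumed share:

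- 20% gives 26.1 cases and an 80% half-width of 1.2816 × √(0.1875 / 26.1) = 0.109
- 40% gives 52.2 cases and 1.2816 × √(0.1875 / 52.2) = 0.077

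The planned 5 points would need 1.6424 × 0.1875 / 0.0025 = 123.2, so about 124 in situ cases.

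**The case against.** The best defence is that the protocol has more in it than this comparison suggests, and that details may sit in an analysis plan not shown. Much of that stands.

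- Objective (b) names its means, the involvement of healthcare professionals. Timed reading of stored images would need no new patients and no use of the AI in live care. The fair criticism of the time part of (b) is that no procedure is described, not that it cannot be done.
- The expert review has validation of accuracy and clinical relevance as its first purpose. It can address interpretability.
- Increased accuracy in (e), and the Introduction's aim of surpassing visual assessment, could be examined from listed data by setting the AI and the provisional diagnosis each against the confirmatory result. That works only if the confirmatory result does not itself depend on that provisional reading.
- Part of (c) is answerable as accuracy on in situ disease.

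A reader might therefore go too far and infer that four of the six objectives fail outright, or that nothing beyond stand-alone accuracy can be concluded. The documents do not support either: parts of (b), (c) and (e) can be answered or recovered as above. Nor do they support reading the 471 as an arithmetic error or the primary aim as undermined.

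What the defence does not reach is diagnosis time and treatment planning in (e), all of (f), and the causal sense of (c). An analysis plan can define analyses of collected data, but these need an AI-use condition that neither phase contains.

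**Conclusion.** The point holds in a limited form. Diagnosis time and treatment planning in (e), the whole of (f), and the impact wording of (c) concern effects of AI use that the described study does not expose anyone to or measure. The workflow and time parts of (b) have no described procedure or data item. Interpretability, generalizability (d) and the accuracy objective (a) are not affected, and neither is the primary aim.

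The size of the problem is which conclusions are supported; the stated sample size does not change. The one numerical consequence is for (c): as an in situ accuracy question it would rest on roughly 39 cases, with an 80% half-width of about 9 points (8 to 11 points for in situ shares of 40% to 20%). This assumes the sizing prevalence holds in the sample and that the Summary's general invasive share carries over. Case-control recruitment and the balanced dataset in Methodology e) could change both.

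**What to change.** - Move diagnosis time and treatment planning in (e), and all of (f), to future work.
- Do the same for the workflow and time parts of (b), unless a reading procedure on stored images is specified for the time part. Keep interpretability, with the expert review as its source.
- Reword (c) as accuracy on noninvasive (in situ) cases. Report it with its interval and label it descriptive, because Methodology b) does not size it.
- Claim increased accuracy in (e), or superiority to visual assessment (Introduction), only if the AI and the recorded provisional diagnosis are both compared with a confirmatory result that is independent of that reading. Otherwise remove both claims.
- Limit all other conclusions to stand-alone performance and interpretability.

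The cost is narrower claims. The wording changes need no added patients, visits or data. A timed reading of stored images, if chosen, would need reader time but no new patients.

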Manual examination of histopathological images is labor-intensive and taxing. Moreover, there's a significant risk of overlooking small cancerous regions on slides, especially as malignant cells may be sparsely distributed. In this scenario, machine learning-based automated inspection techniques offer rapid and dependable identification of invasive and noninvasive cancerous cells and regions on the slide. [5] Diagnoses heavily depend on the expertise of medical professionals, introducing subjectivity and limited repeatability, with documented inaccuracies even among experienced practitioners.

Traditional vision screening of histopathological images via light microscopy poses risks of misdiagnosis and struggles with accessibility due to time and personnel limitations. The primary focus is on leveraging advanced computational techniques to automate analysis, addressing inherent drawbacks in traditional screening methods. Through AI approaches, our aim is to create a model surpassing the accuracy of visual assessments, providing a reliable and efficient means of identifying transformation zones and detecting early signs of breast abnormalities. Central to our objective is the recognition of the need for scalable and cost-effective solutions, particularly in low-income settings. The proposed AI model seeks to mitigate the shortage of trained personnel by automating breast cancer histopathological image analysis, streamlining screening and enhancing accessibility. Moreover, we aim to incorporate domain adaptation techniques to ensure the model's precision and resilience across diverse health facilities, considering challenges such as resource constraints, equipment variations, and demographic diversity.

- **Objectives:** Our primary goal is to compile a diverse dataset of breast tissue histopathology images, incorporating samples from various sources to ensure representation across patient demographics and imaging equipment. Using this dataset, we aim to develop a robust AI model for automated classification of invasive and noninvasive breast cancer within histopathology images. Specific objectives include:
 - a) Clinical Validation: Evaluate the AI model's performance through comprehensive clinical validation, measuring sensitivity, specificity, and accuracy in classifying invasive and noninvasive breast cancer types in histopathology images.

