- **Methodology:** In the clinic-based approach for histopathological breast cancer screening data collection, patient information will be directly gathered within healthcare facilities to develop an AI algorithm for automated cancer detection. This involves capturing essential metadata and clinical details, including histopathological breast images. Utilizing clinic resources, the collected data will train the AI algorithm, offering insights into abnormal findings likelihood during screening. Notably, privacy is prioritized, excluding personally identifiable information in the data collection process.
 - a) **Study Population:** This investigation comprises a prospective and retrospective case-control study designed to develop and assess an AI-based diagnostic tool for breast cancer detection through visual examination. The patient cohorts will include confirmed breast cancer cases diagnosed via gold standard tests and individuals with breast abnormalities resembling cancer (such as Adenosis, Duct Ectasia, Ductal or Lobular Hyperplasia, Fibroadenomas, Fibrosis, Mastitis, Simple Cysts, or other precancerous lesions), along with corresponding confirmatory test results. Additionally, data from individuals with suspected breast cancer (test status unknown) or normal breast condition will be included to support unsupervised learning. The primary aim is to assess the algorithm's ability to differentiate between these patient categories through analysis of their medical image data.

- **Inclusion criteria:**

- Female patients of age 18 years or older can be selected as subjects.
- Individuals willing to participate in breast cancer screening.
- Availability for biopsy examination.
- Women with no current or prior diagnosis of breast cancer.
- Availability of relevant medical records for confirmation and comparison purposes.

▪ **Exclusion criteria:**

- Pregnant women are excluded due to potential impacts on screening results and the necessity for special considerations during pregnancy.
- Individuals with severe medical conditions or circumstances that may render histopathologic examination inappropriate or unsafe are excluded.
- Patients with conditions that could interfere with the accuracy of screening results are excluded.
- Follow-up screenings are not included in this study.

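### An undefined exclusion tied to the accuracy of results could remove difficult cases, including the cancer mimics the study needs, and risks upward spectrum bias of unknown size

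*Protocol*

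**What the plan says.** The third exclusion criterion in Protocol, Methodology a) Study Population, reads: "Patients with conditions that could interfere with the accuracy of screening results are excluded". No condition is listed, interference is not defined, and the Protocol does not say who decides, when, or with what information. Pregnancy and conditions making the examination unsuitable or unsafe have separate exclusions in the same list, so this line must cover something else.

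The same section enrols "individuals with breast abnormalities resembling cancer" and gives examples such as adenosis, hyperplasia, fibroadenoma, fibrosis and mastitis, together with precancerous lesions. It then says: "The primary aim is to assess the algorithm's ability to differentiate between these patient categories through analysis of their medical image data".

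Objective a) is clinical validation, "measuring sensitivity, specificity, and accuracy in classifying invasive and noninvasive breast cancer types in histopathology images". Methodology f) Statistical Analysis evaluates the same measures. Methodology b) Sample size calculation adds that "we need the medical image samples to reflect the various cancerous, precancerous and normal cases". Objective d) seeks generalizability, "assessing its performance in different regions and healthcare settings for broader clinical applicability".

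**The concern.** An accuracy estimate applies only to the case mix from which it was obtained. A criterion keyed to whether a patient might impair accuracy selects on something close to the quantity being measured. If the excluded patients are harder to classify than the rest, sensitivity or specificity among those who remain is higher than in the patients for whom the tool is intended. A larger sample does not correct this.

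The lesions that resemble cancer are natural candidates for the exclusion, because resemblance to cancer is what makes a cancer classification err. They are also a group the study sets out to include. Two sites could read the same page and act in opposite ways, one enrolling a patient with mastitis and the other excluding her. In the retrospective phase the cases come from the clinic's database of prior screenings, and Methodology d) lists the image, the provisional diagnosis and available test results among the data items. The Protocol does not prevent the criterion from being applied with the answer in view.

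Eligibility is fixed in a protocol rather than left to an analysis plan. Prospective patients who are never enrolled cannot be recovered at analysis.

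**Working it through.** **The plan's own figure.** Methodology b) gives expected sensitivity and specificity 0.75, c = 0.05, prevalence p = 0.261, and "we assume an 80% confidence level". With Z = 1.28:

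- N_sen = 1.28² × 0.75 × 0.25 / (0.05² × 0.261) = 470.8, stated as 471.
- N_spec = 1.28² × 0.75 × 0.25 / (0.05² × 0.739) = 166.3, stated as 166.

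Both figures are reproduced, and c acts as a half-width of 5 points. The sample size does not depend on the exclusion. It serves here only as a yardstick.

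**Expected precision at the target of 500,** if the case mix follows p (Z = 1.2816):

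- Cancers: 500 × 0.261 = 130.5. Half-width for sensitivity = 1.2816 × √(0.1875 / 130.5) = 4.9 points.
- Non-cancers: 500 − 130.5 = 369.5. Half-width for specificity = 1.2816 × √(0.1875 / 369.5) = 2.9 points.

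**Shift caused by the exclusion.** Let 0.75 be the accuracy over the whole class (cancers for sensitivity, non-cancers for specificity). Let f be the share of that class excluded and h the accuracy in those excluded. The accuracy in those who remain is

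(0.75 − f × h) / (1 − f).

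The Protocol gives neither f nor h, so both are assumptions.

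| f | h | Calculation | Remaining accuracy | Shift (points) |
|---|---|---|---|---|
| 10% | 0.60 | (0.75 − 0.06) / 0.90 | 0.767 | +1.7 |
| 10% | 0.40 | (0.75 − 0.04) / 0.90 | 0.789 | +3.9 |
| 20% | 0.60 | (0.75 − 0.12) / 0.80 | 0.7875 | +3.8 |
| 20% | 0.40 | (0.75 − 0.08) / 0.80 | 0.8375 | +8.8 |
| any | 0.75 | (0.75 − 0.75f) / (1 − f) | 0.750 | 0 |

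One of the four non-zero scenarios exceeds the planned 5-point margin. Three of the four exceed the 2.9-point half-width expected for specificity.

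**Share needed to reach 5 points.** Setting f × (0.75 − h) / (1 − f) = 0.05 gives f = 0.05 / (0.80 − h). That is 12.5% of the class at h = 0.40 and 25% at h = 0.60.

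**Which measure is affected.** Take cancer as the positive class, as the sample size calculation does. Dropping benign mimics then acts on specificity and leaves sensitivity largely unchanged. Dropping difficult cancers acts on sensitivity. The overlap visible in the text is with the mimics, so specificity is the more exposed of the two.

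**The case against.** The strongest reply is that the text contains no contradiction. The mimics are included by name, the exclusion names none of them, and a general exclusion is naturally read as giving way to a specific inclusion in the same section. The pregnancy exclusion uses similar language about effects on screening results for a patient state, not for a difficult diagnosis. On that reading the line is aimed at confounding conditions. This stands as far as it goes: a reader might infer that the Protocol contradicts itself, and it does not do so outright. But the reply depends on an interpretation the Protocol does not state.

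A reader might also infer that the line does remove hard cases and does inflate both sensitivity and specificity. The documents do not support that. They do not show who would be excluded or that those patients are harder to classify. If they are no harder, the shift is zero; if they are easier, the estimate falls. Nor do the documents tie the line to difficult cancers in particular.

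The possibility of applying the criterion with the diagnosis in view rests on the Protocol's silence, and working rules may exist elsewhere. It shows what the text permits, not what will happen. Finally, case-control sampling and the balanced dataset planned in Methodology e) already shape the case mix, and the effect of this line cannot be separated from theirs. That limits any claim about size. It does not justify an undefined exclusion as well.

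**Conclusion.** The concern holds as a risk. The criterion is open-ended, refers to the accuracy the study measures, and can literally catch lesions the same section requires. Upward spectrum bias is the likely direction, because the rule is aimed at cases expected to impair accuracy, but the documents do not establish that it will occur. The illustrative range of 1.7 to 8.8 points rests on an overall accuracy of 75%, an excluded share of 10% to 20% of a class, and accuracy of 40% to 60% in those excluded. Only the 75% comes from the Protocol, where it is a planning value. The upper end exceeds the planned 5-point margin and the lower end does not. The line should be changed before data collection starts.

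**What to change.** Replace the criterion with an exclusion limited to technically unreadable slides (no tissue, out of focus, staining failure), judged without knowledge of the final diagnosis or the model output. If a patient-level condition is still meant, list it in advance. State that the cancer mimics and precancerous lesions named in Methodology a) are not excluded by this line. Report the number excluded by reason and by diagnosis, so that readers can judge the effect on each class.

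The cost is one rewritten eligibility line, a blinded readability check and slightly more reporting. Estimated accuracy may be lower than under the present wording.
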